7.7 Methods for Clinical Procedures

Assessment of ER positive breast cancer (Italian sites only)

A tru-cut diagnostic biopsy of the primary tumor will be performed percutaneously with a 14 gauge needle after the administration of local anaesthetic. A single skin incision serving both biopsies with the tip of an n.11 scalpel will be performed. Among women who require a biopsy to determined eligibility, the method used to guide the biopsy (guidance with palpation or radiological imaging) will vary with clinical presentation.

The biopsy will be fixed in 10% neutral-buffered formalin for 6-8 hours before being embedded in paraffin. Sections (4-micron thick) are cut, de-waxed and stained with hematoxylin and eosin for conventional histopathological examination (presence and prevalence of normal, hyperplastic, in situ and cancer tissue, grading of the tumor and occurrence of peritumoral vascular invasion) and IHC for the assessment of the ER (mandatory), PgR (optional), Ki-67 labeling index (optional), HER-2 expression (optional).

IEO centralized evaluation of immunohistochemical (IHC) biomarker analyses (All Sites)

Pathology reports of breast biopsy and definitive surgery will be collected by each site.

Tissue samples will be required from both the initial diagnostic breast biopsy (US sites) and the

subsequent surgical excisional procedure. A formalin-fixed and paraffin-embedded (FFPE) block or 6 unstained slides from each time point will be stored locally before shipping to IEO at the end of the study (or more frequently in the case of unstained slides – please refer to the Manual of Operations and Procedures for complete instructions).

It is advised that whenever possible FFPE blocks should be stored locally, and slides to be used for IHC biomarker analyses should be prepared not earlier than one week before shipping in order to avoid antigen decay potentially affecting the IHC procedures. If that is not possible, slides may be cut per institutional practice and stored. Six 5-micron thick sections will be cut from FFPE block and mounted on charged slides, kept in the dark (i.e., in a covered box) and kept at room temperature (18-22°C, 64-71°F) till shipment.

At IEO, every set of slides will be stained by H&E and evaluated for expression of ER, PgR, Her-2 and Ki-67. The IHC analysis will run by using an automated immunostainer (Dako) and the FDA-approved kits Pharm-DX (for ER and PgR) and Herceptest (both by Dako). For Ki-67, we will use the MIB-1 antibody from Dako. The extent of immunostaining will be evaluated strictly following the ASCO-CAP guidelines and the recommendations of the Ki-67 working group (45).

Procedures at the time of surgery (all sites)

At the time of surgery a small but representative sample of the excised cancerous tissue will be obtained, as well as a specimen of adjacent and distant grossly benign tissue for study biomarkers.

8. CRITERIA FOR EVALUATION AND ENDPOINT DEFINITION

8.1 Primary Endpoint

For the purpose of the main endpoint, percent change in serum estradiol concentrations, we will refer to an outsource laboratory (Quest Diagnostics, San Juan Capistrano, CA), that has obtained a CLIA certificate for their high sensitivity estradiol test and will perform estradiol measurements. The method applied is based on LC-MS/MS technology, able to measure down to 2 pg/ml.

We expect to achieve with 25 mg three times a week and 25 mg once a week similar effects in estradiol reductions to the standard dose of 25 mg daily.

8.2 Secondary Endpoints

We will investigate the effects of alternative dosing of exemestane on the following secondary endpoints: (see Section 13.5 for a detailed statistical analysis):

- Exemestane safety and toxicity will be evaluated at the clinic visit according to the Common Terminology Criteria for Adverse Events v4.0 (CTCAE) and by a self-administered Quality of Life questionnaire (MENQOL).
- Change in Ki-67 expression comparing pre-treatment versus post-treatment specimen to compare the antiproliferative effect among the different doses.
- Serum drug measurements of exemestane and 17-dihydroxyexemestane at the end of treatment.
- Additional validated method of estradiol measurement. This method has a lower detection limit (1 pg/ml) than the CLIA certified estradiol test (Quest) and will serve as a quality control since it has proven to more effectively detect estradiol concentrations at the very low level, which is characteristic of older postmenopausal women.

- Serum concentrations of estrone, estrone-sulfate, will be measured by LC-MS/MS while androstenedione and testosterone will be measured by RIA. Sex hormone binding globulin serum levels will be measured by a chemiluminescent microparticle immunoassay (CMIA) on the ARCHITECT *i* System (Abbott Laboratories, Weisbaden, Germany).
- Insulin concentrations will be measured with the Architect Immunoassay analyzer (Abbott Laboratories, Abbott Park, IL, US). Glucose will be measured at each local lab
- Adipokines: change in leptin and adiponectin serum concentrations will be analyzed and compared among the different treatments arms. These measurements will be performed by the use of commercially available enzyme linked immunoassays purchased from R&D systems (SPACE Import-Export Srl, Milan, Italy).
- Lipid profile (total cholesterol, HDL and triglycerides) will be determined locally at baseline and before surgery. Measurement of breast tissue estradiol concentration in tumor and normal breast at time of surgery.
- Centralized evaluation of ER, PgR, Her2 and Ki67 expression in tumor comparing pre-treatment levels (tru-cut biopsy) to post-treatment level expression (surgical specimen).
- Centralized evaluation of Ki-67 in adjacent intraepithelial neoplasia and or grossly benign tissue.
- Drug measurements of exemestane and 17-dihydroxyexemestane on frozen tissue samples, when available.
- Proteomic analysis will be performed with the new Fusion Tribrid mass spectrometer in [name] Shared Resource for the Herbert Irving Comprehensive Cancer Center (HICCC) at CUMC.
- To analyze the UGT2B17 gene we will use Taqman copy number variation assay (Life Technologies, Monza, Italy).
- Crown like structures in mammary fat tissue by IHC (CD68), comparing pre-treatment (tru-cut biopsy) versus post-treatment (surgical specimens).

8.3 Off-Agent Criteria

Participants may stop taking study agent for the following reasons: completed the protocol-prescribed intervention, adverse event or serious adverse event, inadequate agent supply, non-compliance, concomitant medications, medical contraindications. Participants will continue to be followed, if possible, for safety reasons and in order to collect endpoint data according to the schedule of events. Participants will not be replaced.

8.4 Off-Study Criteria

Participants may go 'off-study' for the following reasons: the protocol intervention and any protocol-required follow-up period is completed, adverse event/serious adverse event, lost to follow-up, non-compliance, concomitant medication, medical contraindication, withdraw consent, death, determination of ineligibility (including screen failure).

8.5 Study Termination

NCI, DCP as the study sponsor has the right to discontinue the study at any time.

9. CORRELATIVE/SPECIAL STUDIES

We will collect and process flash frozen tissue, paraffin-embedded tissue, serum and whole blood for evaluation of biomarkers.

9.1 Rationale for Methodology Selection

Estradiol

Serum estradiol concentrations will be determined by use of a CLIA certified test, according to MD Anderson policies for primary endpoint analyses. This test is based on a non-derivatized LC-MS/MS technology that has a detection limit of 2 pg/ml, a limit that may not be sufficient to detect estradiol levels in all postmenopausal women. Any samples that have estradiol results below the detection limit will be assigned to have a concentration of ½ the value of the detection limit.

Because of the critical issue of sensitivity of the method, we have decided to include an additional validated bioanalytical method performed in a CLIA certified laboratory for steroid testing. Estradiol will be measured by a two-dimensional liquid chromatography with mass spectrometry detection LC-MS/MS) after liquid-liquid extraction. Duplicate standard curves, water blanks and four assay control pools are processed with samples to assess accuracy and precision of the assay. This method has a lower detection limit (1 pg/ml) than the CLIA certified estradiol test (Quest) and will serve as a quality control since it has proven to more effectively detect estradiol concentrations at the very low level, characteristic of older postmenopausal women. The functional sensitivity of the test is 1 pg/ml and the within assay precision of two control samples were 13% at 1.0 pg/mL and 8.8% at 5 pg/mL, respectively.

Ki-67

Ki-67 labeling index modulation in preoperative studies has proven to be an appropriate surrogate marker for outcome in participants who are administered antiestrogen therapies.

The Division of Pathology at IEO is in strict compliance with the recommendations of the International Working Group for Ki-67 assessment in breast cancer (45) and performs central revision of Ki67 within the International Breast Cancer Study Group. Ki-67 labeling index expression will be evaluated by IHC, as previously described (46). Specifically, Ki-67 is assessed by IHC according to recent international recommendations (45) using the Mib-1 monoclonal antibody (1:50 dilution; Dako, Denmark), using an automated immunostainer (Dako). We will evaluate all the cells in the diagnostic biopsies, and 2000 cells from three high power (×400) microscopic fields randomly selected at the periphery of the tumor in surgical samples, as previously reported (46). The Ki-67 labeling index is calculated as the percentage of Ki-67 immunoreactive cells over the total number of counted cells.

ER, PgR and HER2

Centralized analyses of ER, PgR (PharmDX) and Her2 (herceptest) expression will be determined by IHC on tumor sections from biopsy and surgical samples, as previously described(45).

Estrone, estrone-sulfate

Estrone will be measured by a two-dimensional liquid chromatography with mass spectrometry detection LC-MS/MS) after liquid-liquid extraction. Duplicate standard curves (2.5-00 pg/mL), water blanks and four assay control pools are processed with samples to assess accuracy and precision of the assay. The detection limit of the assay is 2.5 pg/mL and the intra and inter-assay coefficient of variation of a pooled human serum sample of 21 pg/mL were 4.8% and 9.0%, respectively.

Estrone-sulfate will be measured by a two-dimensional liquid chromatography (HPLC) with triple quadrupole mass spectrometry detection. Estrone-sulfate from serum is first partially purified by protein precipitation, and then further purified by gradient reverse phase HPLC. Duplicate standard curves (10-1000 ng/dL), water blanks and four assay control pools are processed with samples to assess accuracy and

precision of the assay. The detection limit of the assay is 10 ng/dL and the intra and inter-assay coefficient of variation of a pooled human serum sample of 25 ng/dL were 3.6% and 9.3%, respectively.

Androstenedione

Serum concentrations of androstenedione will be measured by a radioimmunoassay kit (DSL-3800 ACTIVE, Beckman Coulter S.r.l., Rome, Italy), containing androstenedione coated tubes. The procedure follows the basic principle of radioimmunoassays where there is competition between a radioactive and a non-radioactive antigen for a fixed number of antibody binding sites. The amount of I^{125} -labeled androstenedione bound to the antibody is inversely proportional to the concentration of androstenedione present in the sample. The separation of free and bound antigen is achieved by decanting the antibody-coated tubes. The sensitivity of the assay is 0.03 ng/mL and the intra and inter-assay coefficients of variation of a control provided with the kit (0.5 ng/mL) were 10% and 14% respectively. Interassay coefficients of variation of our in-house prepared serum pool (1.6 ng/mL) was 14% for androstenedione.

Testosterone

Serum testosterone will be determined by an electrochemiluminescent immunometric assay (Roche Diagnostics S.p.A., Monza, Italy) designed for the Cobas e411 automated analyzer. The sensitivity of the assays was 2.5 ng/dL and the inter-assay coefficient of variation of our in-housed pooled serum sample (18 ng/dL) was 4.6.

Sex hormone binding globulin (SHBG)

Serum concentrations of SHBG will be determined by a chemiluminescent microparticle immunoassay (CMIA) on the ARCHITECT *i* System (Abbott Laboratories, Weisbaden, Germany). This assay shows very good agreement with our previously adopted platforms and the assay performance in terms of reproducibility were improved. Sensitivity of the method is ≤ 0.01 nmol/L and intra and inter-assay coefficient of variation were below 5.5% at 3 different control levels (low, median, high).

Insulin

Serum concentrations of insulin will be determined by a chemiluminescent microparticle immunoassay (CMIA) on the ARCHITECT *i* System (Abbott Laboratories, Weisbaden, Germany). This assay shows very good agreement with our previously adopted platforms and the assay performance in terms of reproducibility were improved. The sensitivity of the method is ≤ 1.0 μ U/mL, and inter-assay coefficient of variation are below 2% at 3 different control levels (low, median, high) produced by Abbott. Interassay coefficient of variation of our in-house prepared serum pool (mean: 4.9 μ U/mL) is 3.9%.

Adiponectin and leptin

Serum adiponectin and leptin will be measured using a commercial enzyme-linked immunosorbent assay kit (R&D Systems, Minneapolis, MN). Serum samples should not undergo freeze and thaw cycles before adiponectin and leptin measurements. Particularly, leptin is very sensitive to freeze-thaw cycles and will be determined after first thaw.

The minimum detectable dose of adiponectin is 0.25 ng/mL and the inter-assay coefficient of variation of our in-house prepared serum pool (mean: 12.5 μ g/mL) was 6.9%. The minimum detectable dose of leptin is 7.8 pg/mL. and the inter-assay coefficient of variation of our in-house prepared serum pool (mean: 9.7 ng/mL) was 6.6%.

Pharmacokinetics

EXE and 17-dihydroEXE concentrations will be determined by mass spectrometry (MS) using Waters® Xevo™ TQ MS in electrospray positive ionization mode (Waters, Manchester, UK), optimized by multiple reaction monitoring mode. We used Zorbax Eclipse Plus C18 columns and mobile phase

MeOH/H₂O with 0.1% formic acid. EXE pure substance was provided by Pfizer Inc., 17 β -hydroxy EXE and EXE-19-d3 were purchased from Toronto Research Chemicals (Toronto, Ontario, Canada).

Proteomic Analysis

Fresh frozen tumor tissues will be homogenized and quantified using the standard operating protocols established in HICCC Proteomics Shared Resource. Exosomes will be isolated from serum using SBI's ExoQuick exosome kit (47-49), and the enrichment of exosomes will be verified by Western blot. 100 μ g of exosomes from each time point of the same participant will be proteolytically cleaved with trypsin and then chemically labeled with mass spectrometer detectable quantification reagent, TMT isobaric mass tags (TMT126, 127, 128, 129)(50,51) separately for quantification. 10 μ g from each TMT labeled sample (4plex) will be mixed per LC-MS/MS run. Three technical replications will be performed per sample. For the LC-MS/MS analysis, 40 μ g of TMT-labeled peptide mixture will be separated by nano-HPLC and analyzed by the new Orbitrap Fusion Tribrid mass spectrometer. The proposed proteomic studies will take advantage of its vastly improved sensitivity, as well as other features that can be optimized for complex samples. For example, parallelization of the newly designed instrument maximizes the amount of high-quality data acquired by synchronizing operations of several different mass analyzers. Dynamic scan management enables selection, sorting, and routing of precursors to different fragmentation modes, enabling us to optimize the instrument for PTM characterization. Also, synchronous MS3 precursor selection significantly increases the number of peptides accurately quantified in isobaric mass tagging experiments. The new Orbitrap Fusion Tribrid mass spectrometer has increased sensitivity for detecting lower abundant proteins, which allows us to use less starting material and increase the number of biological replications for analysis.

Pharmacogenetics

DNA will be extracted from whole blood EDTA treated samples (Qiagen, Italy). We will use Taqman copy number variation assay (Life Technologies, Monza, Italy) for the UGT2B17 genotyping. The expected minor allele frequency (UGT2B17 deletion) in the Caucasian population is 0.26. We recently demonstrated a statistically significant association of the UGT2B17 gene deletion with increased serum concentrations of 17-dihydroxyEXE (Johansson et al. SABCS 2014) in a pre-surgical trial involving 47 participants randomized to exemestane 25 mg/daily for six weeks, exemestane levels were also higher, although the difference was not statistically significant between groups (homozygous wt *versus* heterozygous and homozygous UGT2B17 deleted).

Crown like structures (CLS)

We will use CD68 (mouse monoclonal KP1 antibody; Dako; dilution 1:4,000) to identify CLS in mammary fat tissue in FFPE sections stained by H&E. All cases will be reviewed by the same breast histopathologist. Light microscopy will be used to assess for evidence of CLS.

Biorepository

Leftover specimens will be stored for future unspecified analyses. Leftover samples will be retained at IEO Central Biobank if informed consent for biobanking is signed.

Biologic specimens collected during the conduct of the trial that are not used during the course of the study will be considered deliverables under the contract and thus the property of the NCI. At study completion, NCI reserves the option to either retain or relinquish ownership of the unused biologic specimens. If NCI retains ownership of specimens, the Contractor shall collect, verify and transfer the requested biologic specimens from the site to a NCI-specified repository or laboratory at NCI's expense.

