6.9 Blinding and Unblinding Methods

- Participants will be blinded to exemestane schedule.
- The Statistician and the Site Study Pharmacist will not be blinded to exemestane schedule.
- All other Investigators will be blinded to exemestane schedule.
- All participants will take 1 tablet per day.
- Study assignments will be unblinded to the Study Investigators and Site Coordinators after all of the data are collected and the study database has been locked. Unblinding will also occur if the participant's physician deems that unblinding is necessary, such as in the case of unacceptable toxicity thought to be related to the study agent or progressive disease.
- The Data and Safety Monitoring Board will also be blinded unless unblinding is warranted (if the participant's physician deems that unblinding is necessary, if the participant becomes pregnant, or after all of the data are collected and the study database has been locked).
- Unblinding will only take place after consultation with the NCI, DCP Task Order Monitor (Medical Monitor). Unblinding will be conducted as follows:

- 1) The Site Investigator contacts the Protocol Principal Investigator and requests the participant's treatment status be unblinded.
- 2) The Protocol Principal Investigator contacts the NCI, DCP Task Order Monitor (Medical Monitor) and requests the participant's treatment status be unblinded. The Protocol Principal Investigator then conveys the Task Order Monitor's decision to the Site Investigator. The Site Investigator then proceeds with unblinding as written out below.

- 3) If the NCI Task Order Monitor cannot be reached and the participant requires emergency care, the Protocol Principal Investigator may authorize the Site Investigator to break the blind.
- 4) If the Site Investigator is unable to reach the Protocol Principal Investigator and the participant requires emergency care, then the Site Investigator must proceed with unblinding as written out below.
- 5) The Site Investigator requests the participant's treatment status be unblinded by the research pharmacist (or designated individual responsible for dispensing drug).
- 6) The Site Investigator officially takes the participant off-study.
- 7) The date and reason for breaking the blind must be submitted by the Site Investigator to the Protocol Principal Investigator, [name], as soon as possible.

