13.4 Primary Objective, Endpoint(s), Analysis Plan

Primary objective and primary endpoint

Since the primary objective of this study is to assess if the reduction in estradiol with the standard dose is comparable with the other lower doses, we will measure the estradiol before and after treatment. Thus, the primary endpoint is the percentage change of serum estradiol concentration from baseline and we will compare the median change and percentage changes among arms.

We choose the percentage change as the primary endpoint because it will improve generalization of results, given the wide variability among different assays, and because we predict that a large percentage of participants will have the final values of estradiol below the detectable level.

Analysis plan

We will present full distribution and median values of estradiol at baseline (before treatment), at post (after treatment), and changes and percentage changes (with interquartile ranges) of estradiol level, from baseline to post, by arms. Differences by arms of % change, change and final values will be tested considering t-test and ANCOVA models. Estradiol at baseline will be included as explanatory variable together with other possible confounders such as BMI, age and time since last dose. Normal distribution of residuals from full model will be checked and, if needed, a transformation will be considered.

We will also compare percentages of participants with final values of estradiol below the detectable level by arms with Chi-square tests and logistic models.

We will carry out the two comparisons with the standard dose considering $\alpha=0.025$.

Power analysis

Given the expected reduction of at least 80% change with exemestane at 25 mg daily (56) considered as reference group (control arm) against 25 mg 3 times a week, or 25 mg weekly, for the power calculation we assume a non-inferiority difference of 6% in percentage changes of estradiol after treatment from baseline, using a one-sided, two-sample t-test. A total sample size of 162 participants (54 participants per arm), enables us to achieve 80% power with a margin of equivalence of -6% in the mean percentage changes from baseline at the lower dose compared to the standard dose. The true difference between the means percentage changes is assumed to be 0.0%.

The significance level of the test is 0.025 to take into account of multiple comparisons (we will compare the changes at the two low doses with the standard dose)(57).

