13.6 Reporting and Exclusions

The primary analysis will employ an intention-to-treat approach, which includes all women irrespective of compliance. An according-to-protocol subgroup analysis will be restricted to women who are “compliant”, such as participants who have taken $\geq 80\%$ of the active scheduled pills, and notably, due to the different arm schedule, $\geq 80\%$ of the active pills has to be reached also in the last 7 days before surgery.

Due to limitations of estradiol analysis procedures, small concentrations cannot be precisely measured. These concentrations are said to be below the limit of detection (LOD). We will consider a statistical method that uses the characteristics of the distribution of the values above the LOD to estimate the values below the LOD. This can be done with an extrapolation technique or maximum likelihood estimation that has smaller error rates than all the standard replacement techniques (Methods of Dealing with Values Below the Limit of Detection using SAS. Croghan et al.).

Patterns of observations for covariates will be classified as complete cases (no missingness), terminal (monotone) dropouts, intermittent (non-monotone) dropouts, mixed and no-data. Kendall’s τ_b will be computed in order to test the correlation between a dichotomous indicator of missing observations and treatment assigned as well as any possible baseline covariates.

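### Half-limit substitution, the only definite rule for undetectable estradiol, can favour non-inferiority under heavy censoring, and section 13.4 does not say whether it governs the primary test

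*Combined protocol and SAP*

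**What the plan says.** Section 9.1 (Estradiol) ties the primary endpoint to an assay with a 2 pg/ml detection limit. Estradiol "will be determined by use of a CLIA certified test, according to MD Anderson policies for primary endpoint analyses". The same paragraph calls this "a limit that may not be sufficient to detect estradiol levels in all postmenopausal women" and then fixes the rule for non-detects: "estradiol results below the detection limit will be assigned to have a concentration of ½ the value of the detection limit".

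Section 13.6, after the intention-to-treat statement, turns to the same problem: "We will consider a statistical method that uses the characteristics of the distribution of the values above the LOD". It offers an extrapolation technique or "maximum likelihood estimation that has smaller error rates than all the standard replacement techniques".

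Section 13.4 makes percentage change in serum estradiol the primary endpoint. It plans t-tests and ANCOVA with baseline estradiol, BMI, age and time since last dose as possible covariates, and sets a 6-point margin. Part of its reason for choosing percentage change is that "we predict that a large percentage of participants will have the final values of estradiol below the detectable level". It does not say how those values enter the primary test. No section ranks the two rules or labels either one a sensitivity analysis.

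Section 6.9 adds: "The Statistician and the Site Study Pharmacist will not be blinded to exemestane schedule".

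**The concern.** Half-limit substitution is one of the replacement techniques that section 13.6 calls less accurate. The plan's apparent default is thus a method that its own statistical section ranks as inferior, in a trial that expects many non-detects.

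For a woman with detectable baseline B and an undetectable final value, the rule depends on B alone. Two schedules that suppress estradiol to different depths below 2 pg/ml score the same. In a superiority trial this would cost power. In a non-inferiority trial it can pull the arms together and produce the claim. Because the rule is not settled in section 13.4, it could also be settled after the arms are known.

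**Working it through.** **1. The plan's own figure.** Inputs from section 13.4: margin 6, SD 11, true difference 0, one-sided alpha 0.025, power 80%. Normal approximation: n = 2 × (1.960 + 0.842)² × 11² / 6² = 52.8, so 53 per arm. The exact t calculation gives 54, with power 0.802. Dropout: 162 / 0.90 = 180. The stated sample size reproduces, but it treats percentage change as fully observed.

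**2. The scoring rule.** With B at or above 2 and a final value below 2, the score is 100(1/B − 1):
- B = 3: −67%
- B = 5: −80%, for any true reduction above 60%
- B = 8: −87.5%, for any true reduction above 75%
- B = 10: −90%, for any true reduction above 80%

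A woman undetectable at both visits scores 0%.

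Take true reductions of 80% and 74%. At B = 5 the final values are 1.0 and 1.3 pg/ml. Both become 1, so the 6-point difference becomes 0. At B = 15 they are 3.0 and 3.9 pg/ml, both measured, and the difference survives. Everything therefore turns on the baseline distribution, which the documents do not give.

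**3. Expected censoring.** Section 13.4 predicts a large percentage of non-detects. Section 2.3 puts levels on aromatase inhibitors below 5 pmol/L. Assuming 272.4 g/mol, 5 × 272.4 / 1000 = 1.36 pg/ml, which is under the limit. This is an upper bound for the drug class and says nothing about baseline.

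**4. False non-inferiority at the margin.** Assumed: lognormal baseline, 54 per arm, reductions 80% v 74%, SD 11, values below 2 set to 1 at both visits, one-sided 0.025 test against 6 points, 6,000 simulated trials per cell.

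| Median baseline (pg/ml) | Geometric SD 1.3 | 1.6 | 2.0 |
|---|---|---|---|
| 5 | 70% | 28% | 12% |
| 6.8 | 21% | 20% | 12% |
| 8 | 10% | 13% | 11% |
| 10 | 4% | 7% | 8% |
| 15 | 2% | 3% | 4% |

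Fully measured values give 2.1-2.6%. Independent repeats agree within about two points. The mean apparent difference at medians 5-10 is 1.8-5.5 points instead of 6. Linear adjustment for baseline does not remove the effect (4-74% at medians 5-10).

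With lognormal residuals, median 6 and log-SD 0.5, 81% and 70% of final values are censored. The difference shrinks from 6.0 to 2.9 points, and false non-inferiority is 22% (t-test) or 23% (ANCOVA).

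**5. Deeper suppression.** Section 13.4 expects a reduction of at least 80%. At 90% v 84% with an assumed SD of 7, false non-inferiority is 18-26% even at median 15, where 69-73% of daily-arm final values are censored.

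**6. Power at no true difference.**
- Half-limit, medians 5-10: 80-97% at geometric SD 1.3, 55-84% at 1.6, 25-66% at 2.0.
- Left-censored likelihood at 2 pg/ml, 80% reductions, whole grid, women undetectable at baseline left out: power 11-66%, false non-inferiority 0.3-3.4%. A second implementation gave about 2-4% error where the truth was at the margin.
- Left-censored likelihood at 90% reductions (assumed SD 7), median 5, geometric SD 1.3: at least one arm had no detectable final value in 83-91% of runs, and power was about 1%.

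**The case against.** The strongest reply is that the rule is not really open. Section 9.1 is definite, is attached to the assay designated for the primary endpoint, and is the only firm instruction on non-detects; section 13.6 merely keeps an alternative in view. That stands. A reader might infer that the plan gives no guidance on non-detects, and the text does not support that. What remains is that no precedence is stated, and that the default is one the statistical section itself ranks below likelihood.

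The second reply is that the size is assumed. This also stands. A reader might take 70% as the trial's error rate, but that is one corner cell. At the same median with geometric SD 2.0 the figure is 12%, and at median 15 with 80% v 74% the inflation nearly vanishes. In one lightly censored case (median 15, log-SD 0.3) the difference was slightly exaggerated, at 6.4 points, and the error was 1.4%. The SD of 7 is also an assumption, since section 13.4 gives 11.

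Third, section 13.4 also compares final values and the proportions below the limit, and a second assay reads down to 1 pg/ml. These would show how heavy the censoring is. They carry no margin, the second assay is described as quality control, and none of them governs the primary test.

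Fourth, a reader might infer from section 6.9 that the rule will be picked to suit the result. The documents show only the opportunity. It adds urgency to pre-specification and is not a separate error.

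**Conclusion.** The concern holds in conditional form. The two sections are unreconciled, section 13.4 does not say which rule governs the primary test, and the only definite rule can favour non-inferiority when many final values are undetectable, which the plan itself predicts.

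At 80% v 74%, SD 11 and geometric SD 1.3-2.0, allowing for differences between repeated simulations, false non-inferiority is about 12-70% at a median baseline of 5 pg/ml, 9-13% at 8, 4-9% at 10 and 2-5% at 15. Confidence is high in the conflict and in the direction under heavy censoring. It is not high in the size, which rests on an assumed baseline. The documents do not support saying that the primary test is invalid whatever the baseline, or that one particular model is the only remedy. Because the choice of rule can change the primary conclusion, it should be settled before analysis.

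**What to change.** In section 13.4, before any post-treatment estradiol result is linked to arm:

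1. Name one primary non-detect rule that covers both baseline and final values.
2. Label the other rule and the 1 pg/ml assay as sensitivity analyses.
3. Restate the 80% power under the chosen rule and the expected censoring.

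Left-censored maximum likelihood, which section 13.6 already favours, is the leading option because it keeps the error near nominal. Each undetectable final value can enter as a percentage change at or below 100(2/B − 1), with the 6-point margin unchanged. If it is chosen:
- keep the covariates of section 13.4, including age and time since last dose, or justify any change;
- state how women undetectable at baseline are handled (0-9% in the assumed grid), since they add little to such a model while the intention-to-treat set "includes all women irrespective of compliance";
- give a fallback for an arm with few or no detectable final values.

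If half-limit substitution stays primary, state that it can favour non-inferiority under heavy censoring, and require the censored analysis to agree before non-inferiority is concluded.

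The programming is small; the real cost is power. Under the likelihood rule it may fall well below 80%, so 180 women may not give a conclusive result. Making the 1 pg/ml assay primary is a separate choice. Censored likelihood on it gave about 43-80% power with 0-4.3% error in the assumed grid, but it departs from the test that section 9.1 designates by policy.
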